
Name of Sponsor/Company: Endo Pharmaceuticals Inc.
Name of Investigational Product: EN3319 Oxymorphone HCl Immediate-Release Oral Liquid
Name of Active Ingredient: Oxymorphone HCl

Pharmacokinetic Analysis: Pharmacokinetic variables (Single-Dose Phase: C_{max}, T_{max}, C_{12}, AUC_{0-t}, AUC_{0-24}, $AUC_{0-\infty}$, λ_n, $t_{1/2}$, CL/F, and V/F; Multiple-Dose Phase: C_{max}, T_{max}, AUC_{0-t}, λ_n, $t_{1/2}$, CL/F, and V/F) will be estimated from the plasma concentration data using standard non-compartmental methods. Actual sample times, rather than scheduled times, will be used in the computation of pharmacokinetic parameters. The definitions and methods of determination for each pharmacokinetic variable are summarized in Table 7.
 
Pharmacokinetic variables (CL/F, V/F, λ_n, and $t_{1/2}$, and dose normalized C_{max}, C_{12}, AUC_{0-24}, AUC_{0-t}, $AUC_{0-\infty}$) will be summarized by age group using N, mean, standard deviation (SD), geometric mean, CV, minimum, median, and maximum following dosing in the Single-Dose Phase and the first and third doses in the Multiple-Dose Phase. In addition, a 2-sided 95% CI will be constructed for both CL/F and V/F. T_{max} will be summarized by age group using median, minimum, and maximum.

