In the Single-Dose Phase, as each treatment cohort of subjects within each age group is completed, the effectiveness, safety, and tolerability will be assessed by the IDMC before enrolling subjects into the next-higher treatment cohort. The IDMC will also provide recommendation on whether the subsequent treatment cohorts are needed in the Single-Dose Phase (up to 3 treatment cohorts in total may be tested in the Single-Dose Phase). If needed, non-oxycodone, non-oxymorphone rescue analgesia will be available according to SOC at each institution. Blood from a patent line (see section 12.4.1) will be collected to assess pharmacokinetics, examine dose proportionality, and estimate effective and safe dosing. An opioid antagonist (eg, naloxone-based) will be readily available for immediate intravenous administration at the discretion of the Investigator; subjects requiring naloxone rescue will be discontinued from the study.

Multiple-Dose Phase

At the end of the Single-Dose Phase for each age group, the IDMC will make recommendations for up to 3 dose levels to be used in the Multiple-Dose Phase. The Multiple-Dose Phase will proceed using the same age group stratification used in the Single-Dose Phase:

- A. 6 years to \leq 12 years
- B. 2 years to $<$ 6 years

Age groups A and B will be studied in parallel. Following postoperative parenteral analgesia, when oral dosing is to commence according to each institution's SOC, dosing will begin at the lowest dose selected by the IDMC based on results from the Single-Dose Phase for each age group. Subjects will be dosed every 4 to 6 hours (no sooner than every 4 hours and no later than every 6 hours) for up to 48 hours. Subjects may receive non-oxycodone, non-oxymorphone rescue medication and discontinue from the study in the event that the study drug does not provide adequate pain relief.

[figure not shown]

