7.1.5. Multiple-Dose Phase Assessments and Procedures

The following assessments and procedures will be performed during the Multiple-Dose Phase (see [Table 4](#)) after the baseline assessments have been completed and the subject is dosed. Every effort should be made to collect blood samples at the assigned time intervals relative to the time of administration of study drug:

- Assess and record current pain intensity at 0.5, 1, 1.5, and 2 hrs post-Dose 1, and immediately prior to all remaining Doses administered up through 48 hrs after administration of the initial dose of study drug or until ET or the subject requires rescue medication. Assessments must be made by the Investigator, or designee. Pain will be assessed at time of rescue, but no pain assessments will be completed beyond administration of rescue medication.
- Measurement of vital signs at 0.5, 1, 1.5, and 2 hrs post-Dose 1, and immediately prior to all remaining Doses administered up through 48hrs (or upon ET) after initial administration of study drug.
- Assess respiratory (see section [12.2](#)) and neurological function (see section [12.3](#) and [Appendix A](#)) at 0.5, 1, 1.5, and 2 hrs post-Dose 1, and immediately prior to all remaining Doses administered up through 48hrs (or upon ET) after initial administration of study drug. Assessments must be made by the Investigator, or designee.
- Collection of blood samples for pharmacokinetic assessments at 0.5, 1, 1.5, and 2 hrs post-Dose 1, immediately prior to Doses 2, 3, 4, 5, 6, 7, and at 0.5, 1, 1.5, and 2 hrs post Dose 7..
- Record food consumption: capture the date and time of each consumption of food as well as what was consumed eg, DAT, DAT-soft, CFs, FFs, water from 1 hour prior to first dose of study drug administration through EOS/ET.
- Record rescue medication: provide rescue medication on an as needed basis for BTP. Rescue medication may include opioid-based PCA rescue (but must NOT contain oxycodone or oxymorphone) for as long as the PCA device remains in place per SOC. Oral rescue medications will also be allowed during the study, but also must NOT contain oxycodone or oxymorphone.
- Monitor and document AEs/SAEs throughout the study.
- Update and record concomitant medications (including rescue medications).

Subjects will complete the Multiple-Dose Phase when they complete the EOS assessments and procedures at 48 hours (or upon ET) following initial study drug administration.

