12.4. Pharmacokinetic Assessments

12.4.1. Blood Sample Collections

Blood collection may be performed using an existing line (arterial or venous noted on eCRF) at the start of the study (the use of EMLA[®] at the insertion site is permitted). If access for blood sampling is lost, a new line will only be established as part of the clinical management of the subject; otherwise, the subject's participation in the study will be early terminated. Procedures for blood draws should follow institutional SOC. All catheter lines should be appropriately flushed per institutional SOC prior to each blood draws. The discard volume must be restricted to 0.5 mL for tubing with a dead space of ≤ 0.5 mL and up to 1.0 mL for tubing with a dead space > 0.5 mL. Calculation and evaluation of the following pharmacokinetic variables will be performed for all subjects participating in study: (Single-Dose Phase: C_{max} , T_{max} , AUC_{0-t} , AUC_{0-24} , $AUC_{0-\infty}$, λ_n , $t_{1/2}$, CL/F [clearance], and V/F [volume of distribution]; Multiple-Dose Phase: C_{max} , T_{max} , AUC_{0-t} , λ_n , $t_{1/2}$, and CL/F; see [Table 7](#) for definitions). Blood samples (0.5 mL) will be obtained and placed into 2.0-mL dipotassium ethylenediaminetetraacetic acid (K₂EDTA) tubes at each blood collection time point for both phases (see [Table 3](#) and [Table 4](#)). The samples will be obtained at the following times:

- Single-Dose Phase: Serial blood will be collected at time 0 (Baseline), at 15 and 30 minutes, and at 1, 1.5, 2, 4, 6, 8, 12, and 24 hours post dose.
- Multiple-Dose Phase: Serial blood will be collected at: 0 (Baseline), at 0.5, 1, 1.5, and 2 hrs post-Dose 1, immediately prior to Doses 2, 3, 4, 5, 6, 7, and at 0.5, 1, 1.5, and 2 hrs post Dose 7.

Table 7: Pharmacokinetic Variables

Variable	Definition
C_{\max}	Maximum plasma concentration; the highest concentration observed during a dosage interval
T_{\max}	The time at which C_{\max} was observed
AUC_{0-t}	Area under the concentration versus time curve from time 0 to the last measured concentration (C_t) in the dosing interval, calculated by linear trapezoidal rule
$AUC_{0-\infty}$	Area under the concentration versus time curve from time 0 to infinity, calculated as $AUC_{0-t} + C_t/\lambda_n$
AUC_{0-24}	Area under the concentration versus time curve from time 0 to 24 hours (end of dosing interval)

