λ_n	Terminal rate constant, calculated as the negative slope of the ln-linear portion of the terminal plasma concentration-time curve
$t_{1/2}$	Terminal half-life, calculated as $\lambda_n/(\ln 2)$
CL/F	Apparent oral clearance, calculated as Dose/ $AUC_{0-\text{inf}}$ for single dose or Dose/ $AUC(0-\tau)$ for steady-state
V/F	Apparent volume of distribution, calculated as Dose/ $(AUC_{0-\text{inf}} * \lambda_n)$

Immediately after collection, the tube will be gently inverted several times to mix the anticoagulant with the blood sample. The plasma fraction will be separated by placing the collection tube into a refrigerated centrifuge (4°C to 8°C) for 10 minutes at 1,500 × g. The plasma fraction will be withdrawn by pipette and placed into a polypropylene freezing tube in 1 aliquot for subjects with body weights 3 to 6 kg and in 2 approximately equal aliquots for subjects with body weights greater than 6 kg. All sample collection and freezing tubes will be clearly labeled in a manner that identifies the subject and the collection time. Labels will be fixed to the freezing tubes in a manner that will prevent the label from becoming detached after freezing. All plasma samples will be placed into a freezer at –70°C or below within 1 hour after collection. The additional blood draws for the purposes of pharmacokinetic assessment in this study do not pose more than a minor risk to the subjects.

Total blood volume that will be collected for research purposes, including any discard volume, will be based on the age and weight criteria in section 12.4.2.

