13. STATISTICS

13.1. Sample Size Consideration

The sample size of 6 subjects in each age group (A and B), treatment cohort, and study phase was selected to describe the safety, effectiveness and pharmacokinetic properties of the study drug in children aged 2 to ≤ 12 years. With up to 3 treatment cohorts and 6 subjects per treatment cohort, up to 18 subjects will be enrolled in each study phase. Assuming the %CVs for clearance and volume of distribution are both as high as 72% for pediatric subjects, then with 18 subjects per age group or 36 subjects per study phase, the 2-sided 95% confidence interval (CI) for both clearance and volume of distribution is $(0.71*X, 1.40*X)$, where X represents the geometric mean of either clearance or volume of distribution, respectively. In other words, with 18 subjects per age group or 36 subjects per study phase, the 2-sided 95% CIs are within 60% and 140% of the point estimates for the geometric mean estimates of both clearance and volume of distribution for oxymorphone in all age groups.

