13.6. Pharmacokinetic Analysis

Pharmacokinetic variables (Single-Dose Phase: C_{max} , T_{max} , C_{12} , AUC_{0-t} , AUC_{0-24} , $AUC_{0-\infty}$, λ_n , $t_{1/2}$, CL/F, and V/F; Multiple-Dose Phase: C_{max} , T_{max} , AUC_{0-t} , λ_n , $t_{1/2}$, CL/F, and V/F) will be estimated from the plasma concentration data using standard non-compartmental methods. Actual sample times, rather than scheduled times, will be used in the computation of pharmacokinetic parameters. Plasma concentrations below limit of quantification (BLQ) will be set to zero in the computation of mean concentration values; however, BLQ concentrations between 2 non-BLQ concentrations will be set to missing. For the computation of pharmacokinetic variables, the BLQ concentrations prior to the first measurable concentration

will be set to zero and other BLQ concentrations will be set to missing. The definitions and methods of determination for each pharmacokinetic variable are summarized in [Table 7](#).

Pharmacokinetic variables (CL/F , V/F , λ_n , and $t_{1/2}$, and dose normalized C_{max} , C_{12} , AUC_{0-24} , AUC_{0-t} , $AUC_{0-\infty}$) will be summarized by age group using N, mean, standard deviation (SD), geometric mean, CV, minimum, median, and maximum following dosing in the Single-Dose Phase and the first and third doses in the Multiple-Dose Phase. In addition, a 2-sided 95% CI will be constructed for both CL/F and V/F . T_{max} will be summarized by age group using median, minimum, and maximum.

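### Multiple-Dose PK is to be summarised after the third dose, which has no post-dose profile; Dose 7, which has one, is not named, and as listed its interval is sampled only to 2 h with no rule for completing AUC(0-τ)

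*Combined protocol and SAP*

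**What the plan says.** **Summary occasions.** Section 13.6 summarises CL/F, V/F, the terminal rate constant, half-life and dose-normalised Cmax and AUCs "following dosing in the Single-Dose Phase and the first and third doses in the Multiple-Dose Phase". The synopsis repeats "the first and third doses in the Multiple-Dose Phase".

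**Sampling.** For the Multiple-Dose Phase, Sections 7.1.5 and 12.4.1 agree: baseline, 0.5, 1, 1.5 and 2 h after Dose 1, then "immediately prior to Doses 2, 3, 4, 5, 6, 7, and at 0.5, 1, 1.5, and 2 hrs post Dose 7". Footnote f of Table 4 caps PK samples at 15. Section 7 spaces doses "no sooner than every 4 hours and no later than every 6 hours".

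**Definitions (Table 7, Section 12.4.1).**
- AUC0-t runs to the last measured concentration "in the dosing interval, calculated by linear trapezoidal rule".
- CL/F is "Apparent oral clearance, calculated as" Dose/AUC0-inf for a single dose, or Dose/AUC(0-τ) at steady state. AUC(0-τ) has no entry of its own.
- V/F is "Apparent volume of distribution, calculated as" Dose divided by the product of AUC0-inf and the terminal rate constant.

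**Missing values.** Section 13.6 gives rules only for concentrations below the limit of quantification. Section 13.7 allows no other imputation.

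**The concern.** The summary sentence and the sampling schedule point to different doses. The dose named for the second Multiple-Dose summary has no profile, and the dose with a profile is not named. Moving the summary to Dose 7 is not enough by itself, because the listed samples stop well before the end of the Dose 7 interval and Table 7 needs the AUC over that whole interval.

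Characterising PK is a secondary objective, and the Multiple-Dose Phase (up to 36 children) is the study's only source of repeat-dose PK. Section 13.1 also justifies the sample size by clearance and volume precision, stated as "with 18 subjects per age group or 36 subjects per study phase, the 2-sided 95% CIs", so the Multiple-Dose part of that rationale depends on these estimates. If the text stands, the analyst must choose the dose and the way of completing the AUC after the data are in. A sample that was not drawn cannot be recovered.

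**Working it through.** **1. Reproduce the plan's sample count.** Dose 1 (0, 0.5, 1, 1.5, 2 h) gives 5, pre-Doses 2 to 7 give 6, and post-Dose 7 gives 4. The total is 5 + 6 + 4 = 15, which equals the stated maximum. No draw is left for a Dose 3 profile.

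**2. What each dose can support.**

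| Dose | Samples in its interval | Obtainable |
|---|---|---|
| 1 | 0, 0.5, 1, 1.5, 2 h, pre-Dose 2 | Cmax, Tmax, interval AUC |
| 3 | pre-Dose 3, pre-Dose 4 | two troughs only |
| 7 | pre-dose, 0.5, 1, 1.5, 2 h | Cmax, Tmax, AUC to 2 h |

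**3. Dose 7 coverage, from the documents alone.** Dose 7 falls at 6 × 4 = 24 h to 6 × 6 = 36 h. The unsampled share of the interval is (4 − 2)/4 = 50% to (6 − 2)/6 = 67%.

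**4. Illustration of the AUC at stake.** The documents give no absorption rate or half-life. I assume a one-compartment oral model with ka 0.5–4/h and half-life 2–10 h; τ of 4–6 h is the plan's. With k = ln 2/half-life, the share of one dose's AUC0-inf lying beyond time t is

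R(t) = [ka·e^(−k·t) − k·e^(−ka·t)] / (ka − k).

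*Dose 1, share of AUC0-inf beyond the interval, R(τ):*
- ka 4, half-life 2 h (k = 0.3466), τ 6: (4 × 0.125)/3.653 = 0.137.
- ka 0.5, half-life 10 h (k = 0.0693), τ 4: (0.3789 − 0.0094)/0.4307 = 0.858.

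So about 14–86% must be extrapolated.

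*Dose 7, share of AUC(0-τ) after 2 h,* summing over j = 0 to 6: Σ[R(jτ+2) − R(jτ+τ)] / [1 − R(7τ)].
- ka 4, half-life 2 h, τ 4: 0.2737 × 1.333 = 0.365; the denominator is almost 1.
- ka 0.5, half-life 10 h, τ 6: 0.6262/0.9368 = 0.668.

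So about 37–67% lies after the last listed sample.

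**5. Why AUC0-inf cannot be used after Dose 7.** That AUC still contains drug from Doses 1 to 6. Relative to true CL/F, Dose/AUC0-inf after Dose 7 equals 1/ΣR(jτ), j = 0 to 6. At ka 2/h:
- half-life 2 h, τ 6: 1/1.173 = 0.85.
- half-life 10 h, τ 4: 1/3.628 = 0.28.

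**6. Two ways to close the Dose 7 interval.** Each entry is the linear trapezoid divided by the true AUC(0-τ), at ka 2/h and half-life 2–10 h:

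| End-of-interval value | Result |
|---|---|
| Pre-Dose 8 sample, any mix of 4, 5 and 6 h intervals | 0.99–1.06 |
| Pre-Dose 7 value used as C(τ), equal intervals | 0.98–1.05 |
| Pre-Dose 7 value used as C(τ), varying intervals | 0.92–1.17 |

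**The case against.** **The schedule table may contain the missing sample.** The Table 4 PK row is broken in the available text. It shows 16 marks that cannot be aligned to columns, and one could belong to Doses 8–12. Appendix E, to which footnote f refers, is not available. This stands as a reason for caution: Sections 7.1.5 and 12.4.1 and the maximum of 15 point to no pre-Dose 8 sample, but the source table must settle it. It does not help Dose 3, for which both sections list only the pre-dose draw.

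**The plan already handles this.** Section 13.2 limits PK evaluability to subjects with sufficient concentrations, decided before database lock, and Section 13.6 specifies standard non-compartmental methods. But the evaluability rule cannot supply a profile that was never scheduled. The standard methods do not choose between extrapolating with the terminal slope and carrying a trough forward, and Section 13.7 does not provide for the latter. It is fair that AUC0-t, the AUC listed for this phase, is computable for Dose 7; CL/F as defined is not.

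**'Third dose' might mean the third dose level of Table 6.** That would leave out the second cohort without reason and fits poorly with a phrase about following dosing.

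**The end-of-study sample in Section 7.1.6 might close the interval.** For completers it is drawn at 48 h, which is 12–24 h after Dose 7 and after later doses. It would also be a 16th sample.

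**Stronger readings to avoid.** A reader might infer that the PK objective fails, or that steady-state CL/F is certainly unobservable. The documents do not support the first: the Single-Dose Phase is sampled to 24 h and is unaffected, and Dose 1 interval exposure is obtainable. The second depends on the unverified Table 4 row.

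**Conclusion.** The plan is wrong as written on the summary occasion: a Dose 3 PK profile cannot be produced from the scheduled samples, and this needs no modelling assumption. On the text of Sections 7.1.5 and 12.4.1, 50–67% of the Dose 7 interval is unsampled and AUC(0-τ) has no completion rule. That part is conditional on the source Table 4 and Appendix E showing no pre-Dose 8 draw.

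The AUC shares (about 37–67% for Dose 7, about 14–86% for Dose 1) indicate scale only and rest on the assumed model, ka and half-life. The ranges quoted at ka 2/h would widen if ka were varied. The consequence is a weakened repeat-dose PK description, not a lost objective. It should be fixed.

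**What to change.** 1. **Sections 2 and 13.6:** name the first and seventh doses in place of the first and third.
2. **Sections 7.1.5, 12.4.1 and Table 4:** if the source table has no pre-Dose 8 PK sample, add one in place of one early trough, for example pre-Dose 3, so that the maximum stays 15. Compute Dose 7 AUC(0-τ) and CL/F over the actual Dose 7 to Dose 8 interval. For children already sampled without it, state in 13.6 that the pre-Dose 7 concentration serves as C(τ), flag those whose dosing intervals differed, and note that the approximation worsens as intervals vary.
3. **Section 13.6 and Table 7:** after Dose 7, use Dose/AUC(0-τ) only and label it 'Dose 7 CL/F'. Do not compute AUC0-inf-based CL/F or V/F there. For Dose 1, make Cmax, Tmax and interval AUC the main results. Report AUC0-inf-based CL/F and V/F only with the extrapolated percentage shown, and say that it may be large for most subjects.
4. **Reconcile** Multiple-Dose V/F, listed in Sections 2 and 13.6 but omitted from 12.4.1, and the end-of-study PK sample of 7.1.6 with the 15-sample maximum.

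**Cost:** wording changes and one fewer early trough; pre-Doses 2, 4, 5, 6, 7 and 8 would remain. Dose 8 falls at 7 × 4 = 28 h to 7 × 6 = 42 h, inside the 48 h period, and Section 7.1.5 already schedules vital signs and pain scores before it. Dosing is unchanged.

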Rescue medication ⁿ		As Needed Throughout Study																		
Convert subject to discharge opioid of Investigator's choice																			X	
Schedule 14day follow-up call with site																			X	
Study Completion																				X

FOOTNOTES:

Abbreviations: BL=Baseline; EOS=End-of-Study; ET=Early Termination; IRB=Institutional Review Board; PK=Pharmacokinetic; Pre-Op=Preoperative; Intra-op=Intraoperative

^a Tests results must be available for assessment by the Investigator, or designee, prior to dosing a subject.

^b Investigator, or designee, will train/retrain subjects, parent(s)/legal guardian(s) on the proper use and completion of the pain assessments.

^c Investigator, or designee, will assess if the subject has the cognitive ability to correctly complete the required pain assessments.

^d Pregnancy test (for females of child-bearing potential only) must be completed and the result assessed prior to administration of study drug. Serum βhCG at screening; urine pregnancy test before study drug administration, except if screening occurs in hospital.

^e Dosing times (see section 12.4.1) will vary depending upon the dosing interval.

^f Blood sample drawn before dosing study drug. Maximum number of blood samples for PK is 15 (Appendix E).

^g Clinical labs drawn as part of the SOC will be acceptable for study purposes. Intraoperative labs are acceptable provided they are drawn prior to first surgical incision and assessed by the Investigator prior to administration of the first dose of study drug.

^h Captured following execution of informed consent/assent.

ⁱ Collected by the Investigator for up to 14 days after the last dose of study drug (**documented telephone follow-up required**).

^j See Appendix B and section 9.3 for concomitant medication reporting.

^k A pain assessment will also be completed at the time of rescue immediately prior to rescue medication administration. **No pain assessments will be completed beyond rescue.**

^l Must include type of procedure(s), date of procedure(s), surgical start/stop time, and anesthesia/analgesia start and stop time.

^m Record all times that any food was consumed and what food was consumed (Diet-as-tolerated [DAT], DAT-soft, Full Fluids, Clear Fluids, water) by the subject from 1h prior to dosing through to EOS at 48h post 1st dose/ET.

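### Multiple-Dose first-dose CL/F, V/F and half-life rest on samples that stop at the next dose (4–6 h), with no acceptance rule for slope or extrapolation, and first-dose AUC0-t is pooled over unequal windows

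*Combined protocol and SAP*

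**What the plan says.** **What is reported.** Section 13.6 summarises CL/F, V/F, λn, t½ and dose-normalised Cmax and AUCs by age group "following dosing in the Single-Dose Phase and the first and third doses in the Multiple-Dose Phase". It adds: "In addition, a 2-sided 95% CI will be constructed for both" CL/F and V/F. The Synopsis has the same text.

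**How the parameters are defined (Table 7).** AUC0-∞ is AUC0-t plus the last concentration divided by λn. CL/F is dose over AUC0-∞ for a single dose, and dose over AUC(0-τ) only at steady state. V/F is dose over the product of AUC0-∞ and λn, with no steady-state alternative. AUC0-t ends at the last measured concentration in the dosing interval.

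**What is sampled.** In the Multiple-Dose Phase (Section 12.4.1): "Serial blood will be collected at: 0 (Baseline), at 0.5, 1, 1.5, and 2 hrs post-Dose 1, immediately prior to Doses 2, 3" and so on to Dose 7, followed by four samples in the 2 h after Dose 7. Table 4 caps the count: "Maximum number of blood samples for PK is 15". On the interval, Section 7 says: "Subjects will be dosed every 4 to 6 hours (no sooner than every 4 hours and no later than every 6 hours". The Single-Dose Phase is sampled "at 15 and 30 minutes, and at 1, 1.5, 2, 4, 6, 8, 12, and 24 hours post dose".

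**What is absent.** No section sets a minimum number of terminal points, a minimum time span for the slope, or a maximum extrapolated share of AUC0-∞.

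**The concern.** Dose 1 is not at steady state, so its CL/F and V/F need a terminal slope and an extrapolation to infinity. The profile behind them ends when Dose 2 is given, and nothing is drawn between 2 h and that point. If absorption is still going on at 1.5–2 h, the fitted slope is too shallow, the extrapolated area too large and CL/F too low. The plan has no check that would detect this.

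The resulting values would sit beside Single-Dose values sampled to 24 h, so a reader could take a difference in sampling for a difference between phases. PK characterisation and dosing recommendations are the secondary objectives (Section 6.2), and Section 13.5 also uses the PK analysis in the safety assessment.

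AUC0-t has a separate fault that needs no assumption about half-life. After Dose 1 it stops wherever Dose 2 falls between 4 and 6 h, and the values are then dose-normalised and pooled by age group.

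**Working it through.** **1. The plan's own precision figure.** Section 13.1 gives (0.71X, 1.40X) for the geometric mean of CL/F and V/F at CV 72% with 18 subjects. Using 0.72 as the log SD and a multiplier of 2: exp(±2 × 0.72/√18) = exp(±0.339) = (0.712, 1.404). It reproduces (with 1.96: 0.717, 1.395). It allows for a total log SD of 0.72.

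**2. Sampling count.** 1 baseline + 4 after Dose 1 + 6 pre-dose (Doses 2–7) + 4 after Dose 7 = 15, which matches Table 4. Dose 1 has five post-dose points at most: 0.5, 1, 1.5, 2 h and τ, where τ is 4–6 h. The slope must come from 1.5 h, 2 h and τ, or from 2 h and τ if the peak is at 1.5 h.

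**3. Share of AUC0-∞ beyond τ.** Assumptions, not in the documents: one compartment, half-life 3–10 h, ka 1–3 per h. With k = ln 2/half-life:

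share = ka/(ka − k) × [exp(−kτ) − (k/ka) exp(−ka τ)]

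| | τ = 4 h | τ = 6 h |
|---|---|---|
| ka 3, half-life 3 h (k = 0.231) | 1.083 × 0.397 = 43% | 1.083 × 0.250 = 27% |
| ka 1, half-life 10 h (k = 0.0693) | 1.074 × (0.758 − 0.001) = 81% | 1.074 × 0.660 = 71% |

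Over ka 1–4, the share passes 20% once the half-life exceeds about 1.2–1.6 h (τ = 4 h) or 2.1–2.5 h (τ = 6 h). It passes 50% only above about 2.9–3.7 h or 4.9–5.8 h. With 24 h sampling and ka 2 it is 0–26% for half-lives of 2–12 h.

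**4. CL/F from the Dose 1 times, without noise.** Log-linear slope on 1.5 h, 2 h and τ; linear trapezoid plus C(τ)/λn; result as a ratio to the true CL/F.

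| ka (per h) | CL/F ratio, half-life 3–10 h, τ 4 or 6 h |
|---|---|
| 1–1.5 | 0.16 to 0.95; no value at ka 1, half-life 8–10 h, τ = 4 h, where the fitted line rises |
| 3 | 0.96 to 1.00 |

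The 0.16 is ka 1, half-life 6 h, τ = 4 h: fitted slope 0.013 per h against a true 0.116.

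**5. With assumed 10% assay error, requiring three post-peak points.** Over half-lives of 2–10 h, the share of children with too few points is 86–100% at ka 1, 38–85% at ka 2 and 4–54% at ka 4. Where a slope can be fitted at half-life 8 h and ka 2, geometric-mean CL/F is 0.57 (τ = 4 h) or 0.75 (τ = 6 h) of truth. The estimation log SD is 0.86 or 0.47, to be set against the 0.72 in step 1. At ka 4 and half-life 2–3 h the ratio is 0.96–1.00 with log SD 0.05–0.16, which is usable.

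**6. Unequal AUC0-t windows.** AUC0-6/AUC0-4 = (1 − share at 6 h)/(1 − share at 4 h). At ka 3, half-life 3 h: 0.729/0.570 = 1.28. At ka 1, half-life 10 h: 0.291/0.187 = 1.56. The same child's first-dose AUC0-t would differ by 28–56% depending only on when Dose 2 was given.

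**The case against.** The case on the other side has weight.

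- **A reader might infer that most of AUC0-∞ is extrapolated, from a slope the data cannot give.** The documents do not support this. They state no half-life, and step 3 shows shares below one half within the assumed range. With an early peak three points do exist, and step 4 gives almost no bias at ka 3.
- **A reader might also infer that AUC0-∞ is itself a planned first-dose result.** The phase-specific lists name it for the Single-Dose Phase only. The summary sentence is a pooled list that also contains C12 and AUC0-24, which cannot exist within a 4–6 h interval. AUC0-∞ clearly enters only through Table 7's CL/F and V/F. For V/F, Section 12.4.1 omits it from the Multiple-Dose list that Section 13.6 includes.
- **The CI sentence names no dose.** That it covers the first Multiple-Dose dose is a reading of its place in the paragraph.
- **Section 13.2 limits PK evaluability to children with enough concentration data to calculate the variables.** This can remove profiles with no estimate. It does not stop a poor but calculable slope from being used.
- **The summaries are descriptive and serve a secondary objective.** No hypothesis test depends on them.

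These points limit the size of the claim. They leave in place the dependence on extrapolation, the missing acceptance rule and the unequal AUC0-t windows.

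**Conclusion.** The point holds in a limited form. First-dose CL/F and V/F in the Multiple-Dose Phase depend on a slope from two or three late points and on an extrapolation beyond 4–6 h that the plan does not control. λn and t½ depend on the same slope.

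The bias depends on absorption speed, which the plan does not check: negligible without noise at ka 3, severe or inestimable at ka 1. Large bias is therefore a possibility and not a forecast. All sizes rest on an assumed one-compartment model, half-life and ka; step 5 also assumes the assay error.

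That AUC0-t is pooled over windows of 4 to 6 h follows from the documents alone; only its size (28–56%) rests on the assumptions. AUC0-t still reflects the child's exposure, but mixed with the timing of Dose 2. The plan should be changed; this is not a fatal fault.

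**What to change.** In Section 13.6 and the Synopsis:

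1. For Dose 1 of the Multiple-Dose Phase, report Cmax, Tmax and a partial AUC from 0 to 4 h, interpolated to 4 h with the pre-Dose 2 sample. Limit AUC0-4 to children who have that sample, since some may discontinue or lose the sampling line before Dose 2, and report how many are left out. State what is done when the actual sample time falls just short of 4 h.
2. Do not report CL/F, V/F, λn, t½ or AUC0-∞ for that dose. Take them from the Single-Dose Phase.
3. In the same sentence, reconcile the third dose with Sections 12.4.1 and 7.1.5. There the second serial set follows Dose 7, and Dose 3 has no post-dose sample except the one before Dose 4.

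If the sponsor wishes to keep the first-dose parameters, the weaker alternative is to fix acceptance rules in advance: minimum number of terminal points, minimum span and maximum extrapolated share.

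The cost is wording only, with no extra blood. The downside is fewer first-dose parameters. Because each child enters only one phase, the Single-Dose values come from different children.
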